## 1. Introduction

Ibrexafungerp (formerly “SCY-078”) is a member of a new class of antifungal agents that is being developed as the first oral and intravenous (IV) GSI for the treatment and prevention of fungal diseases caused by *Candida*, *Aspergillus* and other fungal species with the potential to provide the therapeutic advantages of both an IV and oral formulation.

Fungal diseases caused by *Candida* spp., *Aspergillus* spp., *Pneumocystis*, dimorphic fungi, etc., have limited treatment options and represent a growing threat, particularly to patients with compromised immune systems, including patients receiving cancer chemotherapy, hematopoietic stem cell transplantation and solid organ transplantation, and patients with advanced human immunodeficiency virus (HIV)-infection. Invasive fungal diseases caused by *Candida* and *Aspergillus* species are of principal concern. Despite advances in medical care, the overall mortality rate of invasive fungal infections remains high, particularly in the most profoundly immunocompromised patient populations.

Although four classes of antifungal agents are currently available to treat fungal infections, only flucytosine and azoles are available for oral therapy. Concerns about flucytosine toxicity and rapid emergence of resistance on therapy, limits its clinical utility. The emergence of resistance (clinical and mycological) to azoles and more recently to echinocandins and the toxicity associated with polyenes, signals the need for new agents that are well tolerated and that retain activity against resistant strains. Ibrexafungerp has been shown to retain activity against both azole-resistant and, the majority of clinical isolates containing FKS gene mutations, which confer echinocandin resistance. Unlike echinocandins, ibrexafungerp is orally bioavailable, with in vitro and in vivo activity against *Candida*, *Aspergillus* and other fungal genus and, as such, would represent the first oral non-azole treatment alternative for these infections.

This includes e.g. patients with *Candida* infections who are failing therapy clinically or for whom azole therapy is not advisable due to infection with an isolate with a high likelihood of azole non-susceptibility (e.g. *C. glabrata*, *C. krusei*, *C. auris*), or other *Candida* spp. isolates with documented non-susceptibility to azoles based on MIC determination.

Ibrexafungerp has been evaluated by numerous independent laboratories against an extensive panel of clinically relevant yeast and mold isolates. Overall, the epidemiological studies have demonstrated that ibrexafungerp has potent, broad-spectrum activity against the majority of the clinical isolates tested laying the foundation in support of the use of ibrexafungerp for the treatment of invasive fungal diseases.

This study aims to provide evidence of the efficacy and evaluate the safety and Pharmacokinetics (PK) of oral SCY-078 in the treatment of subjects with severe fungal diseases for whom SOC antifungal treatment is not appropriate due to refractoriness, resistance, intolerance, relapse, toxicities, need for oral therapy or other reasons.

The purpose of this statistical analysis plan (SAP) is to ensure the statistical methodologies that will be used are complete and appropriate to allow valid conclusions regarding the study objectives. Results obtained from the analyses outlined in this document will be the basis of the final clinical study report (CSR) for this protocol.

## **2. Study Objectives**

### **2.1 Primary Objectives**

The primary objectives listed below apply to all eligible fungal diseases:

- To evaluate the efficacy of ibrexafungerp in the treatment of severe fungal diseases by a Data Review Committee (DRC) at the primary timepoint for the fungal disease
- To evaluate the safety of ibrexafungerp

### **2.2 Secondary Objectives**

#### **2.2.1 Overall Secondary Objectives**

The overall secondary objectives of the study apply to all eligible fungal diseases:

- To evaluate the efficacy of ibrexafungerp as determined by the DRC at other time points
- To evaluate the efficacy of ibrexafungerp as determined by the Investigator
- To determine the efficacy of ibrexafungerp by pathogen
- To determine the efficacy of ibrexafungerp by fungal disease and disease category (type of fungal disease)
- To evaluate the efficacy of ibrexafungerp by recurrence of the baseline fungal disease
- To evaluate the efficacy of ibrexafungerp by reason for enrollment (refractory, resistance, relapse, intolerance, toxicity, need for oral therapy)
- To determine All-Cause Mortality (ACM)
- To evaluate the pharmacokinetics (PK) of ibrexafungerp by population PK analysis

#### **2.2.2 Disease-Specific Secondary Objectives**

- To evaluate the efficacy of ibrexafungerp as determined by other disease-specific endpoints ([Table 7](#))

## **2.3 Study Design**

This is a multicenter, open-label, non-comparator, single-arm study to evaluate the efficacy, safety and PK of ibrexafungerp in male and female subjects  $\geq 18$  years of age with documented

severe fungal diseases for whom SOC antifungal treatment is not appropriate due to refractoriness, resistance, intolerance, relapse, toxicities, need for oral therapy or other reasons.

Subjects must have a documented eligible fungal disease that has been refractory to, has relapsed after, or subject has intolerance to or demonstrated toxicities resulting from an approved SOC antifungal treatment as listed in [Table 5](#) (Eligible Fungal Diseases), or has an isolate resistant to, or that has a high MIC and is unlikely to respond to antifungal SOC. Subjects are also eligible if, in the judgement of the Investigator, continued IV antifungal therapy is not feasible or desirable due to clinical or logistical circumstances or if other oral antifungal alternatives are not appropriate. Subjects should meet these and other study criteria to be considered for enrollment. Inclusion of each subject in the study must be approved by the Sponsor (or Sponsor designee) prior to initiation of study drug.

The study will be conducted at approximately 40 sites globally and is planned to enroll and treat approximately 220 (+10%) subjects.

## Study Schedule

For all subjects except VVC subjects, there will be a Screening visit, a Baseline visit (also considered Day 1), several scheduled visits depending on the subject's fungal disease, an EOT visit and a follow-up visit 6 weeks after EOT. For ABPA subjects there will be additional follow-up visits 3 months and 6 months after EOT. For CMC, CPA and ABPA subjects there will be a TOC visit on EOT or Day 84 for CMC subjects or Day 90 for CPA and ABPA subjects, whichever comes first. Following Screening, eligible subjects will receive the study drug loading dose on Days 1 and 2 and the study drug maintenance dose from Day 3 up to EOT, for a maximum of 180 days. A summary of the overall treatment and follow-up schedule for these subjects is provided in [Table 1](#).

**Table 1 Summary of Overall Treatment and Follow-Up Schedule for All Subjects Except VVC Subjects**

Pre-study Activities	Ibrexafungerp Loading Dose	Ibrexafungerp Maintenance Dose	TOC	EOT	6-Week Follow-Up	Additional Follow-Ups
Screening a (Days -1 [-3])	Day 1 a (Baseline) & Day 2	Day 3 to EOT	EOT or Day 84 (CMC) EOT or Day 90 (CPA and ABPA) whichever comes first	Last dose of study drug (up to 180 days from Day 1)	6 weeks ( $\pm 7$ days) after EOT	3 and 6 months after EOT for ABPA subjects only

Abbreviations: ABPA = allergic bronchopulmonary aspergillosis; CMC = chronic mucocutaneous candidiasis; CPA = chronic pulmonary aspergillosis; EOT = end of treatment; TOC = test of cure

a: Screening and Baseline (Day 1) may occur on the same day.

Subjects with VVC will have a Screening visit, a Baseline/Day 1 visit, and scheduled visits on [REDACTED], Day 17 (TOC), 25-day FU (Day 32) and 35-day FU (Day 42). VVC subjects will receive treatment [REDACTED] [REDACTED]. The EOT and 35-Day FU visits may be a phone contact for asymptomatic subjects. A summary of the overall treatment and follow-up schedule for VVC subjects is provided in [Table 2](#).

**Table 2      Summary of Overall Treatment and Follow-Up Schedule for VVC Subjects**

Pre-study Activities	Ibrexafungerp Dosing	EOT (Phone/on site)	TOC	25-Day FU	35-Day FU (Phone/on site)
Screening a (Day -1)	[REDACTED]	[REDACTED]	Day 17 ( $\pm 3$ )	Day 32 (25 days after EOT; 32 days after first dose)	Day 42 (35 days after EOT; 42 days after first dose)

Abbreviations: EOT = end of treatment; FU = follow up; TOC = test of cure; VVC = vulvovaginal candidiasis

a: Screening and Baseline (Day 1) may occur on the same day.

## Study Treatments

Eligible subjects (excluding VVC subjects) will receive ibrexafungerp monotherapy given as an initial loading dose of 750 mg BID during the first two days of treatment (Day 1 and Day 2) and then subsequent oral doses of 750 mg QD for up to 180 days depending on fungal disease. Ibrexafungerp given as combination therapy will be required for all subjects with refractory or relapsing invasive pulmonary aspergillosis, mucormycosis and other molds with unpredictable ibrexafungerp activity based on Investigator's judgement and contingent on Sponsor approval. The treatment duration may be extended beyond 180 days, if needed, for certain fungal diseases. Sponsor approval must be obtained for any extension of treatment beyond 180 days. For subjects receiving extended treatment, a 4-week visit schedule may be followed. Subjects who have a recurrence after EOT may also be considered for re enrollment upon discussion with the sponsor. Subjects who are re enrolled will follow the protocol defined visit schedule.

Subjects with VVC will receive oral doses [REDACTED] [REDACTED]. Subjects treated for VVC who have a recurrence after TOC may receive additional cycles of ibrexafungerp treatment, similar to the initial regimen, upon discussion with the sponsor.

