Subjects will receive ibrexafungerp monotherapy given as an initial loading dose of 750 mg (3 tablets of 250 mg each) given BID (total daily dose = 1500 mg) during the first 2 days of treatment and then subsequent oral doses of 750 mg (3 tablets of 250 mg each) QD for up to 180 days, depending on fungal disease. Treatment beyond 180 days may be permitted under certain circumstances to be agreed upon by the Investigator and the Sponsor on a per-subject basis. Subjects may be considered for re-enrollment upon discussion with the sponsor.

If subjects cannot swallow the whole tablet, the tablets may be split. In the event subjects experience gastrointestinal intolerance on the 750 mg QD dose, the tablets may be split and/or administered at 10 to 20-minute intervals. [REDACTED]

Ibrexafungerp Monotherapy for VVC

Subjects with VVC will receive ibrexafungerp monotherapy given as oral doses of [REDACTED] Subjects treated for VVC who have a recurrence may receive additional cycles of ibrexafungerp treatment similar to the initial regimen upon discussion with the Sponsor.

Ibrexafungerp Combination Therapy

Monotherapy with ibrexafungerp is not recommended for refractory or relapsing IPA or mucormycosis. All subjects enrolled for refractory or relapsing IPA or mucormycosis should receive ibrexafungerp given

as combination therapy. Subjects with IPA and intolerance to other SOC options can be considered for enrollment to receive ibrexafungerp monotherapy, upon discussion with the Sponsor.

For subjects who have infections due to other emerging fungi, including yeasts and molds, but have no culture isolate available (to confirm susceptibility to ibrexafungerp), combination therapy should be considered and discussed with the Sponsor. Combination therapy will also be allowed for other subjects based on Investigator's judgement and contingent on Sponsor approval.

Acceptable antifungal therapy includes voriconazole, isavuconazole, posaconazole, or amphotericin B (AMB) at the doses recommended per their label. When used in combination with the azoles, the dose of ibrexafungerp should be reduced from 750 mg to 500 mg.

The following combination options are allowed:

- addition of ibrexafungerp to any ongoing antifungal therapy
- replacement of one (toxic/ineffective) element of a two-antifungal combination therapy with ibrexafungerp
- replacement of current monotherapy with a new combination, generally:

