7.2 Rationale for the Study

This study is being conducted to evaluate the efficacy, safety and PK of ibrexafungerp in male and female subjects ≥ 18 years of age with documented severe fungal diseases for whom SOC antifungal treatment is not appropriate due to refractoriness, resistance, intolerance, relapse, toxicities, need for oral therapy or other reasons.

Eligible subjects must be selected based on study criteria and be approved for selection by the Sponsor or Sponsor designee.

Subjects must have a documented eligible fungal disease that has been refractory to, has relapsed after, or the subject has intolerance to or demonstrated toxicities resulting from an approved SOC antifungal treatment, or has an isolate resistant to, or that has a high MIC and is unlikely to respond to SOC antifungal treatment. Subjects are also eligible if, in the judgement of the Investigator, continued IV antifungal therapy is not feasible or desirable due to clinical or logistical circumstances or if other oral antifungal alternatives are not appropriate. Refractoriness, defined as persistent clinical, radiological or mycological evidence of fungal disease, and intolerance, including presence of, history of or anticipated toxicities (e.g. drug-to-drug interactions) associated with administration of SOC antifungal agents, will be determined by the Investigator.

The primary efficacy endpoint of the study is Global Response (composite assessment of clinical, radiological and mycological responses) as determined by a Data Review Committee (DRC). The primary endpoint will be determined at the TOC visit for VVC, CMC, CPA and ABPA and at the EOT visit for all other fungal diseases.^{7,8} Clinical response will be evaluated by the signs and symptoms of the infection and/or imaging scans, if applicable. Mycological response will be assessed by mycological testing (fungal culture, KOH and other fungal stains, T2 testing) and/or serological testing (including GMI, *Coccidioides* titers, and β -D-glucan levels, among others),⁹ if applicable. Recurrence will be assessed at the 25-Day FU visit (25 days after EOT) for subjects with VVC and at the 6-Week FU visit (42 days after EOT) for all other subjects as a secondary efficacy endpoint. Recurrence is defined as Global Response at EOT (TOC for VVC) but re-emergence of the baseline fungal disease (with the same fungal species and involving the same site) during the post treatment follow-up.

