14.1.2 Enrollment and ID Assignment

At Screening, all subjects who have signed an ICF will receive an 8-digit subject identification (ID) number that will be composed of a 3-digit study number (301) and a 2-digit site number followed by a 3-digit sequentially assigned subject number starting at 001. Subject numbers will be sequentially assigned by the database upon entry by the site. For instance, if site 01 enters the first subject in the database, the subject ID will be 301-01-001. The second subject entered in the database will get the subject number 002 as entered by any site, so that if site 02 enters the second subject, the subject ID will be 301-02-002. This number will be unique to each subject and will be used to identify the subject throughout the study. Non-U.S. sites will have a 3-digit site identification number, instead of a 2-digit number for U.S. sites.

Subjects who are screen failures or who are not eligible for treatment will be recorded as such in the site's subject screening log. The subject numbers assigned to eligible subjects will be recorded on the electronic Case Report Form (eCRF). Only one subject number will be assigned to each eligible subject.

For subjects who signed an ICF (i.e., are assigned a subject number) but were NOT treated because they did not meet all of the inclusion/exclusion criteria, the Screening visit pages of the eCRF will be completed. The criteria that were not met for enrollment will be documented on the eCRF.

All eligible subjects must be approved by the Sponsor (or Sponsor designee) for enrollment. An Eligibility Form will be used to request eligibility confirmation from the Sponsor or Sponsor designee.

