18.4.2.2 Recurrence

Recurrence is defined as Global Response at EOT but re-emergence of the baseline fungal disease during the post treatment follow-up. Re-emergence of the fungal disease is required to be with the same species and involving the same site that was initially identified at Baseline.

Recurrence will be assessed at the 25-Day FU visit (25 days after EOT, 32 days after first dose) for subjects with VVC and at the 6-Week FU (42 days after EOT) for all other subjects as a secondary efficacy endpoint. For CPA subjects, recurrence will also be assessed at Day 180.

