### **3.2 Analysis Populations**

The analysis populations to be used in the analysis are defined as follows:

**Intent-to-Treat Population:** The intent-to-treat (ITT) population will include all subjects who are enrolled in the study and receive at least 1 dose of study drug.

**Myco-ITT:** the Myco-ITT population will include all ITT subjects with confirmed pathogens and who also had all necessary cultures or mycology tests to estimate mycological response.

**Per-Protocol Population:** The per-protocol (PP) population will include all ITT subjects who received enough study drug (ibrexafungerp) to enable clinical efficacy judgement as determined by the DRC, who have an EOT (TOC for VVC, CMC, CPA and ABPA as applicable) assessment and who have no major protocol violations that could impact the assessment of efficacy (Refer to Section 7).

**Safety Population:** The safety population will include all subjects who receive at least one dose of study medication and have at least one safety assessment post Baseline.

**Pharmacokinetic Population:** The pharmacokinetic (PK) population will include all enrolled subjects who provide at least one PK sample and no deviations significant enough to affect the interpretability of PK data.

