### 6.2.1 Study Participation Calculation and Extent of Exposure

The duration of study participation (days) is calculated as date of Study Completion/Termination recorded on the End of Study page – Informed Consent date + 1. If the date of Study Completion/Termination on the End of Study page is missing, or if a subject is lost to follow-up, the latest available visit date will be used.

The duration of study treatment (days) is calculated as the date of the last dose date – the date of the first dose date + 1.

The cumulative doses taken across the treatment period for all fungal diseases will use the exposure and missed dose log. For all fungal diseases, excluding VVC, the dosing regimen is 2 doses on study days 1 and 2 and then 1 dose from study day 3 to EOT. The dosing regimen for VVC is [REDACTED]. The missed dose log will be used to subtract the total number of missed doses from these total cumulative doses.

The duration of study participation, duration of study treatment, and the cumulative doses will be summarized by summary statistics. All this exposure information will be presented in a listing.

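### The plan allows second courses after recurrence, but its duration, dose-count and EOT rules assume one course per subject

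*SAP*

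**What the plan says.** SAP 2.3 (Study Treatments) opens two routes to a second course. For diseases other than VVC, "Subjects who have a recurrence after EOT may also be considered for re enrollment upon discussion with the sponsor", and such subjects then follow the protocol visit schedule again. For VVC, "Subjects treated for VVC who have a recurrence after TOC may receive additional cycles of ibrexafungerp treatment, similar to the initial regimen". No limit on the number of cycles is stated.

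Protocol 18.4.2.2 states: "Recurrence is defined as Global Response at EOT but re-emergence of the baseline fungal disease during the post treatment follow-up". Protocol 7.2 gives the VVC variant: "Recurrence is defined as Global Response at EOT (TOC for VVC) but re-emergence of the baseline fungal disease". One sentence in the synopsis, in the paragraph on monotherapy excluding VVC, is looser: "Subjects may be considered for re-enrollment upon discussion with the sponsor". It does not mention recurrence, although the study-design part of the synopsis and Protocol 12.1.1 do.

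On identification, Protocol 14.1.2 says: "Only one subject number will be assigned to each eligible subject". On populations, SAP 3.2 says: "The intent-to-treat (ITT) population will include all subjects who are enrolled in the study and receive at least 1 dose of study drug".

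On exposure, SAP 6.2.1 begins "The duration of study treatment (days) is calculated as the date of the last dose date" and then subtracts the first dose date and adds 1. For non-VVC diseases its dose count is two per day on Days 1 and 2 and one per day from Day 3 to EOT, less doses in the missed dose log. SAP 3 ties baseline and study day to the first dose of study drug. None of these sections mentions a second course.

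**The concern.** A plan that permits re-treatment has to say which course supplies baseline, exposure and outcome. This one does not, and what goes wrong depends on how a re-treated person is recorded.

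- **One number for both courses.** Treatment duration runs from the first dose of course 1 to the last dose of course 2, so time off drug is reported as time on drug. Baseline and study day stay anchored to course 1, and a disease assessed at EOT has two EOT records.
- **A new number for the second course.** Duration is then correct for each record, but the same person can enter ITT twice. The two outcomes are correlated, while the Clopper-Pearson interval treats them as independent.

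The two faults do not arise together for the same person, but the text leaves both open. At stake are the exposure tables for re-treated subjects and, in small disease categories, the DRC response rate. The study is open-label, so the course rule should be in writing and not left to programming.

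**Working it through.** **Single-course reading of the plan's own figure.** Protocol 10.3 expects about 222 days per subject. The 180-day maximum plus the 6-week follow-up gives 180 + 42 = 222, the length of one course. The planned 220 subjects have no formal calculation behind them, so there is nothing to reproduce there.

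**Duration, one subject number.** The formula is last dose day - first dose day + 1. The VVC span of Days 1 to 7 comes from the synopsis. The 37-day course is the mean in the preliminary review of 20 subjects (Protocol 7.1), where treatment ran from 7 to 90 days. Restart days and gaps are assumptions.

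| Case | SAP formula | Days within courses | Off-drug days counted |
|---|---|---|---|
| VVC, second cycle Days 18-24 | 24 | 14 | 10 |
| VVC, second cycle Days 32-38 | 38 | 14 | 24 |
| VVC, second cycle Days 40-46 | 46 - 1 + 1 = 46 | 7 + 7 = 14 | 32 |
| Two 7-day courses, 42-day gap | 56 | 14 | 42 |
| Two 37-day courses, 14-day gap | 88 | 74 | 14 |
| Two 37-day courses, 42-day gap | 37 + 42 + 37 = 116 | 74 | 42 |
| Two 180-day courses, 42-day gap | 402 | 360 | 42 |

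With a 42-day gap the excess is 300% for two 7-day courses, 57% for two 37-day courses and 12% for two 180-day courses.

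**Dose count, non-VVC.** Take two 37-day courses with a 42-day gap and read EOT as the second one. The rule gives 4 + (116 - 2) = 118 doses. Counted within courses, with the loading days repeated, the total is 2 × (4 + 35) = 78. The 118 arises only if the gap is not entered as missed doses. If EOT is read as the first one, the rule gives 4 + 35 = 39 and drops the second course. The VVC dose rule is redacted and was not tested.

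**Which outcome is primary.**

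- VVC: the primary time point is TOC at Day 17, and extra cycles come only after TOC. This points to the first course.
- CMC, CPA and ABPA: EOT or Day 84/90, whichever is first, with days counted from the first dose. This also points to the first course.
- Invasive candidiasis, EC, OPC, dimorphic fungi, IPA and other emerging fungi: EOT, with no rule for two EOTs.

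**Response rate in an EOT-assessed category.** The 11 successes in 20 are borrowed from the preliminary review as an illustration. Assume 3 are re-treated, all first-course successes, and s of the 3 second courses succeed (s = 0 to 3).

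- First course: 11/20 = 55%.
- Last course: (11 - 3 + s)/20, from 8/20 = 40% to 11/20 = 55%.
- Both as records: (11 + s)/23, from 11/23 = 48% to 14/23 = 61%.

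**Overall rate on the same logic**, starting from an assumed 121/220 = 55.0%:

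| Re-treated | Last course | Both as records |
|---|---|---|
| 5 | 116/220 = 52.7% to 55.0% | 121/225 = 53.8% to 126/225 = 56.0% |
| 20 | 101/220 = 45.9% to 55.0% | 121/240 = 50.4% to 141/240 = 58.8% |

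**The case against.** The strongest reply is that a re-enrolment is a fresh entry. SAP 2.3 has re-enrolled subjects follow the visit schedule, and that schedule (SAP Table 3) includes consent, ID assignment and a new Baseline/Day 1. On that reading each course has its own first dose, and the duration formula contains no gap. This stands as a possible reading, so a reader should not infer that the exposure tables are wrong whatever the record structure. It does not settle the matter: the one-number rule makes no exception for re-enrolment, and SAP 2.3 describes repeat VVC treatment as further cycles.

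The reply also runs that ITT is defined on subjects and the endpoint is a percentage of subjects, so under one number a denominator above the number of people would contradict the text. That stands. Double counting is a risk only if new numbers are issued.

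A reader might infer that every second course comes from a known responder and that the response rate is therefore inflated. The documents do not support this. The looser synopsis sentence omits recurrence, and nothing requires DRC adjudication of the first course before re-enrolment. SAP 7.2.3 can also recode a culture-positive recurrence before the follow-up visit as non-success on the primary assessment. Even when all re-treated subjects were responders, the calculations above run in both directions.

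Two smaller points are fair. The 14 VVC days are a calendar span containing six dosing days, so they are not days of dosing. The study is also exploratory, with no efficacy threshold for a shifted rate to cross.

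**Conclusion.** The point holds in two parts.

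First, under one subject number the stated duration formula overstates treatment by the whole off-drug interval, and the non-VVC dose count has no rule to exclude it. The error per subject equals the gap, so in relative terms it is largest for short courses (46 days against 14 in the VVC example) and modest for long ones (402 against 360).

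Second, for diseases assessed at EOT, the SAP leaves open which course's outcome is primary. In the illustrative category of 20 with 3 re-treated responders, that choice spans 40% to 61% around a first-course rate of 55%. VVC, CMC, CPA and ABPA already have rules that point to the first course.

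These sizes rest on assumed gaps, restart days, course lengths and numbers re-treated. The documents do not say how many subjects were or will be re-treated, so the effect on the overall rate may be small. Neither a systematic upward bias nor an error under every way of recording subjects is established.

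**What to change.** - **SAP 6.2.1:** compute treatment duration as the sum over courses of (last dose date - first dose date + 1), and cumulative doses as the sum of doses within courses. Carry the same rule into planned dose and compliance in SAP 6.2.2.
- **SAP 3.2:** state that each person counts once in each population, whatever number is used on re-enrolment, and that a new number must be linked to the first.
- **SAP 7:** take baseline and the primary outcome (EOT, or TOC where that applies) from the first course. Summarise later courses separately, each with its own baseline.
- **Disposition:** report how many subjects had more than one course.
- **Protocol synopsis:** reconcile the re-enrolment sentence that omits recurrence with the passages that state it.

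The cost is SAP wording and minor programming, plus the synopsis reconciliation. No new data are needed.
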